7.1.4. Study Duration

The total duration of Study 977-311 per subject will be a maximum of 60 months from day of study entry. The end of study is defined as the date of the last visit of the last subject.

7.2. Number of Subjects

Up to approximately 133 subjects transitioned from Study 747-213 or Study 747-214 (or other Sponsor studies) who continue to meet this protocol's requirements.

7.3. Planned Dosing Regimen

Subjects who continue to meet this protocol's requirements will receive the FDC tablet (OCA 5 mg + BZF 400 mg SR), once daily.

7.4. Monitoring and Management of Potential Hepatic Injury and/or Disease Progression

Given the chronic and progressive nature of PBC, it is important to monitor for potential hepatic injury, disease progression, and/or hepatic decompensation. CP and MELD scores will be reviewed at each visit where labs are drawn ([Section 7.4.4](#) and [Section 14.2.1](#)). CP Scores should only be applied in subjects who have evidence of cirrhosis or progression to cirrhosis based on criteria presented in [Section 7.4.4](#). In addition, AEs, signs and symptoms of potential hepatic injury or decompensation, and laboratory values will also be reviewed at regular intervals as described in [Section 7.1.3](#). Based on the assessments of signs and symptoms of hepatic injury and/or muscular injury and liver biochemistry ([Section 7.4.1](#) and [Section 7.4.2](#)), the investigational product (OCA + BZF) may be interrupted or discontinued per the criteria discussed in [Section 7.4.2](#) and [Section 7.4.3](#).

7.4.1. Signs and Symptoms of Hepatic Injury or Decompensation

Subjects should be instructed to contact study personnel immediately if they notice any of the following signs and symptoms or have healthcare interactions outside of the study setting:

- Specific signs and symptoms of liver impairment: e.g., yellowing of the skin or the whites of eyes, pale-colored stools, urine color change from pale to deep amber (dark) (reflecting impaired bilirubin metabolism)
- More general signs and symptoms of ascites and encephalopathy: e.g., confusion, swelling of the legs or abdomen
- Non-specific signs and symptoms of impaired health: e.g., nausea, vomiting, abdominal pain, diarrhea, weight loss, fever, chills, worsening or new fatigue, weakness, loss of appetite
- Significant intercurrent illnesses such as gastroenteritis may exacerbate hepatic injury or decompensation (e.g., established severe abdominal pain, vomiting, and persistent diarrhea) and should be an indication for prompt investigational product interruption and complete subject evaluation

Other Symptoms:

- Worsening of renal function (e.g., reduced urine output) or likely dehydration
- New or worsening baseline myalgias or likely myositis

Healthcare Provider (HCP) Interactions:

- Visits to primary HCP or referral to any specialist for any new symptoms (other than ongoing care for stable comorbidities)
- New medications or changes to current medications prescribed from HCP or any new over the counter medications or herbal supplements
- Laboratory procedures or assessments performed by an HCP

Signs and symptoms for potential hepatic injury or decompensation should be followed by (1) evaluation of liver biochemistry for suspected drug-induced liver injury (DILI) or potential hepatic decompensation, (2) assessment of clinical events for potential hepatic decompensation (Section 7.4.2), (3) triggering of investigational product interruption or discontinuation per criteria (Section 8.4.1), (4) documentation in the AE electronic case report form (eCRF) or the SAE eCRFs (Section 14.1.4.1 and Section 14.1.4.2), and (5) contact with the Medical Monitor (Section 14.1.6).

[figure not shown]
7.4.2. Assessments for Potential Hepatic and/or Muscular Injury or Potential Hepatic Decompensation

Liver biochemistry and serum CK will be assessed to evaluate for potential hepatic and/or muscular injury or hepatic decompensation. These assessments will be performed at:

- Each protocol-specified visit (Table 3)
- Unscheduled visits as needed in the event of signs or symptoms of potential hepatic and/or muscular injury or decompensation or if laboratory alerts have been triggered

It is important that the laboratory assessments be completed as required and that the central laboratory be used for assessments whenever possible. In the event that a subject cannot return to the clinic for a scheduled or unscheduled visit, or there is an event that triggers a need for an immediate assessment, the use of a local lab is permissible at the discretion of the Investigator. In these cases, the Investigator will obtain the laboratory results and the laboratory normal ranges.

The process for assessing criteria is presented in Figure 2, and the specific threshold(s) for each laboratory analyte to trigger investigational product interruption are summarized in Table 5.

Figure 2: Management Algorithm for Potential Hepatic and/or Muscular Injury

CK=creatine kinase; INR=international normalized ratio; IP=Investigational Product; PK=pharmacokinetic

Notes: Laboratory assessments include: ALT, ALP, AST, GGT, direct and total bilirubin, INR, and CK.

PK sampling should be conducted within 7 days of IP interruption; close monitoring including physical exams and repeat biochemistry labs should occur as often as deemed appropriate by the Investigator (Table 4).

Table 4: Laboratory Criteria for Monitoring of Potential Hepatic and Muscular Injury for Interruption^a of Investigational Product

Baseline ^b	Treatment Emergent	Liver Signs and Symptoms ^c
Any value	Any hepatic enzyme elevation (TB, ALP, AST, ALT, GGT)	Yes
ALT or AST Normal	ALT or AST ≥ 3 x ULN and TB ≥ 2 x BL	Yes or No
	ALT or AST ≥ 3 x ULN and INR >1.5	Yes or No
	ALT or AST ≥ 5 x ULN and Any TB	Yes or No
ALT or AST Elevated	ALT or AST ≥ 2 x BL and TB ≥ 2 x BL	Yes or No
	ALT or AST ≥ 2 x BL and INR >1.5	Yes or No
	ALT or AST ≥ 3 x BL (or ≥ 300 U/L, whichever occurs first) and Any TB	Yes or No
TB \leq ULN	TB ≥ 2 x BL and $>$ ULN	Yes or No
TB $>$ ULN	TB ≥ 1.5 x BL or ≥ 3.0 mg/dL, whichever occurs first	Yes or No
ALP \leq ULN	ALP ≥ 2 x BL and $>$ ULN	Yes or No
ALP $>$ ULN	ALP ≥ 2 x BL or ≥ 1000 U/L, whichever occurs first	Yes or No
CK	≥ 5 x ULN or ≥ 3 x ULN with symptoms of rhabdomyolysis ^{d,e}	N/A

BL=baseline; CK=creatinine kinase; DILI=drug-induced liver injury; INR=international normalized ratio; IP=investigational product; N/A=not applicable; TB=total bilirubin

^a Interrupt study drug; Initiate workup of competing etiologies and close monitoring (repeat labs and exam 2-3 times per week), including repeat labs initially.

- Study drug can be restarted after a minimum of 30 days if another etiology is identified, liver enzymes return to baseline, lab abnormalities are determined not to be due to DILI, no symptoms, and approved by the Medical Monitor and Investigator.
- If study drug is restarted after 30 days, repeat labs in 2-5 days for ALT, AST, and TB or 7-10 days for ALP as indicated and continue close monitoring.

^b New baseline values for DILI monitoring for ALT, AST, ALP, TB should be determined based upon average of Month 3 and Month 6 values if average is $>50\%$ decrease from original baseline. Adapted from [Palmer 2020](#).

^c Liver signs and symptoms to include: new onset severe fatigue or significant worsening of baseline fatigue; new onset severe pruritus or significant worsening on baseline pruritus; nausea, vomiting, right upper quadrant pain; fever, rash, or $>5\%$ eosinophilia; new onset of hepatic decompensation (e.g., ascites, variceal bleeding, hepatic encephalopathy).

^d Symptoms of rhabdomyolysis may include muscle swelling; weak, tender or sore muscles; dark urine; fever; tachycardia; nausea and vomiting; confusion; dehydration; or abdominal pain.

^e If IP interrupted due to CK trigger, closely monitor CK and creatinine/renal function in addition to liver biochemistries every 2 weeks until values return to baseline levels; same criteria apply to considering re-initiation of IP. CK levels should be assessed in patients reporting symptoms of rhabdomyolysis, and investigational product should be discontinued if markedly elevated CK levels (≥ 5 x ULN) occur or myopathy is diagnosed.

It should be noted that it is difficult to recognize every potential marker of hepatic deterioration or muscular injury. There is no substitute for good medical judgment. Investigators will be reminded to be cautious and mindful in their evaluation of subjects' symptoms, signs, and laboratory results. However, for example, a single abnormal laboratory analyte result may be artifactual; accordingly, Investigators will be allowed to implement an alternate follow-up procedure if considered appropriate based on their medical judgement but only after documented agreement with the Sponsor's Medical Monitor.

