5.4.2. Bezafibrate

Although BZF is not licensed for treatment of patients with PBC, both the AASLD and European Association for the Study of the Liver (EASL) guidelines for PBC mention the investigational or off-label use of fibrates for the treatment of PBC ([Lindor 2022](#), [EASL 2017](#)).

BZF is a low-solubility-high-permeability drug that is almost completely absorbed following oral administration. BZF has a low volume of distribution, is extensively bound to serum albumin,

and its erythrocyte uptake is minimal. Elimination is rapid. BZF is predominantly (about 50% of the dose) excreted in the urine as unchanged drug. In patients with impaired renal function, especially those patients in whom creatinine clearance (CrCl) is less than 60 mL/min, there is a marked increase in the systemic exposure of BZF. Systemic exposure increases further with decrease in renal function when CrCl is lower than 60 mL/min. When administered together with cholestyramine, the maximum plasma concentration (C_{max}) and area under the plasma concentration-time curve (AUC) values of BZF are reduced, indicating decreases in oral absorption. This effect of cholestyramine can be minimized by waiting 2 hours after cholestyramine intake before administering BZF.

The literature contains various reports of fibrate monotherapy studied in the treatment of PBC, including a systematic review and meta-analysis of 9 clinical trials (total of 269 patients) that evaluated the efficacy and safety of BZF mono-therapy treatment in patients with PBC (Yin 2015) (Appendix A). In total, approximately 610 subjects with PBC have been treated with BZF (400 mg/day) for at least 8 weeks and up to 110 months. When added to background therapy with UDCA in subjects with PBC, BZF has demonstrated efficacy in a large randomized, blinded, placebo-controlled trial (BEZURSO). After 24-months of combined treatment (BZF 400 mg + UDCA), subjects treated with BZF + UDCA had a significantly higher rate of complete biochemical response (defined as normal levels of total bilirubin, ALP, aminotransferases, and albumin, and a normal prothrombin index) than subjects treated with placebo + UDCA (31% versus 0%) (Corpechot 2018).

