5.5.2.2. Bezafibrate Dose

BZF is a pan-PPAR (α , δ , γ) agonist approved in multiple non-US countries for the treatment of various primary and secondary hyperlipidemias. Standard dosages include the IR 200 mg tablet formulation administered up to 3 times daily (600 mg/day) or the sustained release (SR) 400 mg tablet formulation administered once daily (400 mg/day).

SR 400 mg is the daily dose of marketed BZF being assessed in this study. The BZF dose-response data were obtained from patients with hyperlipidemia using triglycerides and/or cholesterol as response markers. The lowest available marketed BZF dosage is the 200 mg IR tablet, which has a relatively short 2.4-hour half-life. Based on the dose-response data from (Wolfram 1980), this dose would show less than maximal reductions in triglycerides and cholesterol in a hyperlipidemia population. For example, where a 400 mg/day BZF dose caused an estimated 18% reduction in triglycerides relative to placebo, a 200 mg/day dose caused a 9% reduction (Wolfram 1980). Nine review studies (Yin 2015) and the controlled trial of BZF (Corpechot 2018) used BZF at a dosage of 400 mg/day, suggesting that this is the highest dose of interest, and thus will be used in the current study.

A significant effect of BZF in combination with UDCA on ALP was seen as early as 1 month following initiation of treatment (Akbar 2005). Other studies have demonstrated that a significant effect was seen within 3 months of treatment (Yin 2015).

In an analysis of the ITT population, in both Study 747-213 (BZF 400 mg SR \pm OCA) and Study 747-214 (BZF 400 mg IR \pm OCA), BZF 400 mg SR demonstrated ability to lower ALP and total bilirubin and improve tolerability (pruritus) at Month 3. In all instances, regardless of formulation and combination with OCA, BZF 400 mg led to greater reductions in ALP and total bilirubin relative to BZF 100 mg and 200 mg at Month 3. Across all treatment groups and irrespective of OCA or BZF dose or formulation, TEAEs were balanced across both Study 747-213 and Study 747-214. Collectively, the greatest improvement in ALP, total bilirubin, and tolerability was achieved with 400 mg BZF SR.

All subjects will be transitioned to the OCA + BZF FDC tablet (OCA 5 mg + BZF 400 mg SR) once daily dose upon rolling over to this study.

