13.1. PK Blood Sampling

All PK blood collections must be performed at the clinical site and not at a local lab.

Subjects need to be in fasting condition for at least 8 hours prior to collection of PK samples. A [REDACTED] through Month 60 (EOS), and the ET and/or Unscheduled Visits (if applicable). A [REDACTED] also must be collected within 7 days of a safety event (e.g., event related to potential hepatic or muscular injury).

The acceptable windows for sample collection on Month 1 through Month 60 Visits are shown in Table 7. There is no window required for the Day 1 Visit as investigational product will not be administered.

Table 7: Acceptable Windows for Pharmacokinetic Sample Collection (Month 1 through Month 60)

Nominal Sampling Time	Acceptable Sampling Window
[REDACTED]	30 minutes ±15 minutes before dosing

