14.1.5. Overdose

An overdose is defined as administration of a quantity of a medicinal product given per administration or cumulatively that is above the maximum recommended dose according to the authorized product information. When applying this definition, clinical judgement should always be applied (EMA 2017). The event of overdose should be carefully assessed and reported (e.g., intent, exposure, signs, symptoms, and potential confounders). PK sample must be collected. Patient-reported history of overdose must be assessed and documented regarding intent, exposure, and potential co-ingestants.

Per the CCDS v5.0, in clinical trials, patients with PBC who received OCA 25 mg QD (2.5-times the highest recommended dosage) or 50 mg QD (5-times the highest recommended dosage) experienced a dose-dependent increase in the incidence of hepatic adverse reactions, including elevations in liver biochemical tests (transaminase and bilirubin up to greater than 3x ULN), ascites, jaundice, portal hypertension, and PBC flares.

While there has been no reported case of overdosage in treatment with BZF, symptomatic and supportive measures should be taken. Because BZF is highly bound to plasma proteins, hemodialysis should not be considered. In patients with existing impaired renal function, if dosage recommendations are not followed, overdosage may occur and severe rhabdomyolysis may develop. Administration of BZF must be stopped immediately and renal function must be carefully monitored.

In the case of overdose, patients should be carefully observed and supportive care administered, as appropriate.

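### The event-driven PK rules set no time from the last dose, so once dosing stops a sample taken late in the 7-day window cannot show bezafibrate exposure at the event

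*Protocol*

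**What the plan says.** Several places in the protocol govern PK samples prompted by an event:

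- **Section 7.4.2, Figure 2 notes:** "PK sampling should be conducted within 7 days of IP interruption". The clock starts at interruption and the verb is *should*.
- **Section 13.1:** a sample "also must be collected within 7 days of a safety event". The clock starts at the event and the verb is *must*.
- **Section 14.1.5 (overdose):** "PK sample must be collected", with no time limit.
- **Table 3 notes and Section 9.7.3:** a PK sample is requested at an unscheduled visit made for a safety event, again with no time from the last dose.

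Routine samples are timed tightly by comparison. Table 7 places them 30 ± 15 minutes before dosing from Month 1 to Month 60.

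On bezafibrate kinetics, Section 5.5.2.2 gives one figure: "The lowest available marketed BZF dosage is the 200 mg IR tablet, which has a relatively short 2.4-hour half-life". The study uses another formulation: "SR 400 mg is the daily dose of marketed BZF being assessed in this study". Section 10.1 describes a release-controlling agent in the tablet, and no half-life is given for it. Section 5.4.2 calls elimination rapid and says that when creatinine clearance is below 60 mL/min "there is a marked increase in the systemic exposure of BZF".

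Appendix B (row for Section 13.1) gives exposure-safety analysis as the reason for adding PK at unscheduled visits.

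**The concern.** Muscle toxicity is a bezafibrate risk named in Table 2, which links it to impaired renal function. For a CK or renal event, a reviewer wants to know whether bezafibrate exposure was high when the event occurred. A Table 4 trigger leads to interruption, and the rules then allow the sample up to a week later. A near-zero bezafibrate result at that point reflects time off drug, but it could be read as low exposure.

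Two uses are at stake:

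- **Causality.** Table 8 lets a drug level measured in body fluids support the highest causality category. A late draw removes that evidence for bezafibrate.
- **Pooled exposure-safety work.** If samples taken one day and seven days off drug are combined, differences between subjects mostly reflect sampling delay.

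No rule flags the problem. The PK Population removes only samples affected by major deviations, and a day-7 draw is compliant.

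**Working it through.** **Inputs**
- Window: 7 days = 168 h (Section 7.4.2 Figure 2 notes; Section 13.1).
- Half-life: 2.4 h, immediate-release 200 mg tablet (Section 5.5.2.2).
- Sustained-release half-life: not in the documents. Assumed 6 to 12 h, with 24 h as a stress case.
- Dosing: once daily. Routine PK is about 0.5 h before a dose, so about 23.5 h after the previous one.

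**Formulae.** Half-lives elapsed: n = t / t½. Fraction remaining: 2^(−n). This assumes first-order decline from the last dose. A sustained-release tablet goes on releasing drug for a time, and the longer assumed half-lives are meant to cover that.

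| t½ (h) | Half-lives by day 7 | Left at 24 h | Left at 48 h | Left at day 7 |
|---|---|---|---|---|
| 2.4 (IR, stated) | 168/2.4 = 70 | 0.1% | 0.0001% | 8.5 × 10⁻²² |
| 6 (assumed) | 168/6 = 28 | 6.25% | 0.4% | 3.7 × 10⁻⁹ |
| 12 (assumed) | 168/12 = 14 | 25% | 6.25% | 6.1 × 10⁻⁵ (0.006%) |
| 24 (stress case) | 168/24 = 7 | 50% | 25% | 0.8% |

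**How slow would elimination have to be?** For 1% to remain at day 7, t½ = 168 × ln 2 / ln 100 = 25.3 h, about 10.5 times the stated figure (25.3/2.4). For 10% to remain, t½ = 168 × ln 2 / ln 10 = 50.6 h.

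**Effect of timing alone.** Take two subjects with identical exposure, one sampled 24 h and the other 168 h after the last dose. They differ by (168 − 24)/12 = 12 half-lives at 12 h, a ratio of 2¹² = 4,096. Even at 24 h the ratio is 2⁶ = 64. Both samples comply.

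**Early samples are different.** At an assumed 6 to 12 h, a 24 h draw keeps 6% to 25%, so it can be interpreted if the time since last dose is known.

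**OCA.** Section 5.4.1 describes prolonged exposure. Appendix B (contraception row) says 30 days exceeds five OCA half-lives, so the half-life is below 30/5 = 6 days. At that bound 2^(−7/6) = 45% remains at day 7. This is only an upper bound, but it shows why a 7-day limit may still be useful for OCA.

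**The case against.** The strongest reply is that seven days is an outer limit and not the sampling time. Table 3 notes and Section 9.7.3 already ask for PK at the safety-event visit, and Table 4 footnote a calls for repeat labs two to three times a week after interruption. An early sample is therefore both compliant and likely. A trigger found at a scheduled visit also has that visit's pre-dose sample, taken before interruption. Both points stand, and they narrow the gap to events between scheduled visits that are sampled late. Visits are six months apart after Month 6, so such events will occur.

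A reader might infer several stronger things that the documents do not support:

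- **That 70 half-lives describes the study tablet.** The 2.4 h figure belongs to another formulation.
- **That late samples will be below quantification in nearly everyone.** No assay limit is given.
- **That accumulation would certainly be missed.** Renal impairment may slow elimination, and no half-life is given for it.
- **That any sample within seven days of an event is uninformative.** If dosing continues after the event, the sample is still on-drug. The decay argument starts only when dosing stops.
- **That the planned tables are distorted.** SAP Section 5.5 analyses scheduled visits only and lists the rest, and Protocol Section 15.6 commits to listings and descriptive summaries.

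Part of Section 13.1 is redacted, Figure 2 is not shown, and sample handling is left to separate manuals. The time of last dose may already be recorded somewhere.

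**Conclusion.** The point holds for late samples after dosing has stopped. The rules accept a sample that cannot show bezafibrate exposure at the event, and their clocks start at different points. The conclusion does not depend on the missing sustained-release half-life: day 7 is 14 to 28 half-lives at an assumed 6 to 12 h, and less than 1% remains even at 24 h. It would weaken only if the apparent half-life were well above 25 h, for example in marked renal impairment.

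The consequence is limited. It falls on causality assessment of individual events and on any exposure-safety or population PK work reported separately. The SAP summaries are unaffected. This is an inexpensive improvement to an existing rule, worth making because an event sample cannot be taken again later.

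**What to change.** 1. Align the Table 3 notes, the Figure 2 notes in Section 7.4.2, and Sections 9.7.3, 13.1 and 14.1.5 on one rule: draw the PK sample at the first on-site blood draw made for the event, as near to the last dose as practicable. Keep seven days only as the outer limit, which may still serve OCA.
2. Record the date and time of the last dose and of the sample, if not already captured.
3. Report event samples with time since last dose. Pre-state a limit, set from the sustained-release tablet's half-life and the assay limit, beyond which a sample is not evaluable for bezafibrate and is not reported as low exposure. As an illustration, five half-lives (3.1% left) would be 30 to 60 h at the assumed 6 to 12 h.

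**Cost.** Small changes to protocol and manual wording, and at most a few eCRF time fields. A site sample is already required, so no added visit is generally needed, though some will have to come earlier. Table 4 footnote e sets CK follow-up every two weeks, so those repeat labs alone do not guarantee an early draw. Events first assessed at a local laboratory may still give late samples, because Section 13.1 requires PK collection at the site. No dose or stopping rule changes.

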Notes: Unscheduled visits should occur as needed in the event of signs or symptoms of suspected hepatic injury or decompensation or if laboratory alerts have been triggered. Subjects who discontinue investigational product but continue in the study may be requested to come in for an Unscheduled Visit at the discretion of the Investigator depending on the timing of their next scheduled study visit. Unscheduled visits are optional and should occur as needed based on Investigator discretion; a PK sample should be collected if an unscheduled visit occurs due to a safety event.

^a The Day 2 Visit can be either a virtual or onsite visit. It will be scheduled on Day 2 to Day 7 of the study depending on when laboratory results are available and reviewed. Subjects can elect to pickup IP onsite (onsite Day 2 visit) or have it shipped directly to them (virtual Day 2 visit). For subjects that have IP shipped, the Day 2 virtual visit should be scheduled once the subject receives IP.

^b An ET visit should occur in subjects who withdraw from the study. The ET visit should be completed as near as possible to the subject's last dose of IP. Study procedures and assessments are not required if previously completed within 4 weeks of the ET.

^c Subjects should be instructed to fast overnight (at least 8 hours) before all in-clinic study visits, but water is permitted. Record fasting status in the source and eCRF. If the subject reports having eaten or drunk anything other than water within 8 hours, document accordingly in the source and eCRF and remind the subject that fasting is required before all onsite study visits.

^d On the Day 2 Visit, the Investigator will review Day 1 eligibility laboratory results. If any laboratory results are out of range, the Medical Monitor and Sponsor Medical Monitor will review and determine an appropriate plan for the subject on a case-by-case basis.

^e If subjects develop myopathy at any point during the study, CK values must be checked. A CK $\geq 5 \times$ ULN or $\geq 3 \times$ ULN with symptoms consistent with rhabdomyolysis will require investigational product interruption. Laboratory values including CK and creatinine will be closely monitored every 2 weeks until values return to baseline levels.

^f Waist-to-hip ratio will be calculated via EDC from waist and hip circumference measurement.

^g Body temperature, sitting heart rate, respiratory rate, and seated blood pressure after sitting for 3 minutes.

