7.4.4.3. Potential Myopathy Evaluation and Monitoring

Subjects will be monitored for potential myopathy events throughout the study. If a subject becomes aware of the development of signs and symptoms of potential myopathy (i.e., muscle weakness, muscle soreness or muscle pain), the subject will be instructed to promptly contact the site for further assessment.

Clinical criteria for the monitoring of these events and the interruption/discontinuation of investigational product is as follows:

- At Day 1/Day 2: Check baseline CK: If ≥ 5 x ULN the Medical Monitor and Sponsor Medical Monitor will determine if the subject can continue in Study 977-311 on a case-by-case basis.
- Previous History of Myalgia: Yes or No. If Yes, rate on a scale of 1 to 10 with 1 being the least amount of discomfort and 10 being the most amount of discomfort to establish baseline.
- If subjects develop symptoms of myopathy at any point during the study, CK values must be checked. A CK ≥ 5 x ULN or ≥ 3 x ULN with symptoms consistent with rhabdomyolysis will require investigational product interruption. Laboratory values including CK and creatinine will be closely monitored until values return to baseline levels (see [Table 4](#)).

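### After a CK-triggered interruption the protocol gives two retest frequencies 4- to 6-fold apart, plus Investigator discretion; after a liver trigger it gives one fixed frequency and open discretion

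*Protocol*

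**What the plan says.** Four places in the protocol govern repeat testing after investigational product is interrupted for a laboratory trigger.

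- **Section 7.4.2, Figure 2 note** (hepatic and/or muscular injury): "close monitoring including physical exams and repeat biochemistry labs should occur as often as deemed appropriate by the Investigator (Table 4". No number is given, and the sentence ends by pointing to Table 4.
- **Section 7.4.2, Table 4 footnote a.** Its marker sits on the table title, "Laboratory Criteria for Monitoring of Potential Hepatic and Muscular Injury for Interruption". The instruction is "Initiate workup of competing etiologies and close monitoring (repeat labs and exam 2-3 times per week), including repeat labs initially". The same footnote sets a 30-day minimum before restart.
- **Section 7.4.2, Table 4 footnote e**, on the CK row and limited to a CK trigger: "closely monitor CK and creatinine/renal function in addition to liver biochemistries every 2 weeks until values return to baseline levels". It adds that the restart criteria are the same.
- **Section 7.1.3, Table 3 footnote e**, on myopathy and CK: "Laboratory values including CK and creatinine will be closely monitored every 2 weeks until values return to baseline levels".

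Two further texts bear on these. Section 7.4.4.3 repeats the CK instruction without an interval ("Laboratory values including CK and creatinine will be closely monitored until values return to baseline levels") and refers to Table 4. The paragraph after Table 4 lets an Investigator use an alternate follow-up procedure, "but only after documented agreement with the Sponsor's Medical Monitor".

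**The concern.** A site with a CK-triggered interruption can find three instructions for the same event: several tests a week, one test every two weeks, or whatever the Investigator judges right. A site with a liver trigger finds a fixed frequency in Table 4 that can be varied only with documented agreement. It also finds a figure note that grants discretion without that agreement. A monitor could not say whether sparser testing is a protocol deviation.

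Long-term safety is the primary objective. Under footnote a, restart depends on liver enzymes returning to baseline and on a judgement that the abnormality is not drug-induced liver injury. Adjudication (Section 14.3) works from whatever source documentation exists. If sites test at different rates, those decisions rest on different amounts of information, and a worsening subject may be recognised later at one site than at another. With about 133 subjects at about 60 sites (133/60 = 2.2 per site), most sites will see few such events and will rely on the written text.

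**Working it through.** The documents state no ratio or test count, so there is no plan figure to reproduce. The check is which rule reaches which trigger, then how far the numeric rules differ.

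**Scope**

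| Source | Liver trigger | CK trigger |
|---|---|---|
| Table 4 footnote a (on the title) | 2 to 3 per week | 2 to 3 per week, if the title marker reaches the CK row |
| Table 4 footnote e (CK row) | does not apply | 1 per 2 weeks |
| Table 3 footnote e (myopathy/CK) | does not apply | 1 per 2 weeks |
| Figure 2 note | Investigator discretion | Investigator discretion |
| Section 7.4.4.3 | does not apply | no interval; refers to Table 4 |

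**CK trigger, per 14 days**

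- Footnote a: 2 × 2 = 4 tests to 3 × 2 = 6 tests.
- Footnote e: 1 test.
- Ratio: 4/1 = 4 to 6/1 = 6.

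**CK trigger, over the 30-day minimum hold**

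- Footnote a at a constant rate: 2 × 30/7 = 8.6 to 3 × 30/7 = 12.9 tests.
- Footnote e: 30/14 = 2.1 tests.
- Ratio: again 4 to 6.

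**Assumption.** These figures hold the weekly rate constant. Footnote a's closing word, *initially*, leaves open that the rate applies only at first, and no end point or later rate is given. As arithmetic only, and not as a suggested schedule: suppose the higher rate lasted one week and testing then went to every two weeks for the remaining 23 days. The count would be 2 + 23/14 = 3.6 to 3 + 23/14 = 4.6, against 2.1, a ratio of 1.7 to 2.2. The 4- to 6-fold figure is therefore the constant-rate case.

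**Liver trigger.** The only number is 2 to 3 per week. The alternative is unnumbered discretion, so no ratio exists. The conflict is one of rule: a fixed frequency with documented agreement needed to depart from it, against free choice.

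**The case against.** **Footnote e is the specific rule for CK.** The rest of footnote a is written about the liver, footnote e gives its own interval, and Table 3 footnote e repeats that interval. Footnote e carries the restart criteria over to CK, which would be redundant if all of footnote a already governed that row. This is a plausible reading, but the protocol does not state it. Footnote a is attached to a title that names muscular injury, and footnote e covers liver biochemistries too, so the same tests carry two frequencies. The reading also leaves the Figure 2 conflict for liver triggers untouched.

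**The Figure 2 note defers to Table 4.** It may, but it hands the frequency to the Investigator and then cites a table that fixes one. The drawing itself was not available in the text reviewed, so whether it separates liver from CK triggers is unknown.

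**The intensive rate is only for the start.** This stands as a limit on the size. Section 7.4.3, on decompensation events, spells out a step-down to a frequency set by clinical status; footnote a does not.

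**Existing controls limit variation.** Medical Monitor contact (Section 7.4.1) and follow-up of possible liver injury to normal or baseline (Section 14.1.9) do help. Neither sets a test frequency.

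**Stronger readings a reader might infer.** One is that the two-week interval also competes for liver triggers, giving a six-fold spread for any interruption. Both two-week texts are confined to CK or myopathy, and six is only the upper end for CK. Another is that the reported hepatic and muscle safety results depend on which sentence a site followed. The restart criteria mention no peak value, and the adjudication definitions sit in charters outside these documents. SAP Section 5.5 analyses scheduled visits only and sends unscheduled ones to listings. The worst-value shift tables and the Hy's law count in SAP Section 10.3 might look sensitive to extra tests, but Section 5.5 as written keeps those tests out. The hepatic-injury and myalgia events of special interest are defined by MedDRA terms.

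**Conclusion.** The inconsistency is real and should be corrected; it is one of wording. For a CK-triggered interruption, the two numeric rules differ 4- to 6-fold, with Investigator discretion as a third instruction. That size assumes footnote a reaches the CK row and its rate is held constant; the protocol settles neither. For a liver trigger there is one number and a conflicting grant of discretion, with no computable ratio. The supported consequence is uneven follow-up of suspected injury between sites, and of the labs that inform restart and adjudication. An effect on the SAP's by-visit summaries is not shown.

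**What to change.** Reconcile the Figure 2 note, Table 4 footnotes a and e, Table 3 footnote e and Section 7.4.4.3:

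1. State whether footnote a's testing frequency applies to the CK row, and how long that frequency lasts.
2. Give one frequency for each trigger type (liver, CK), in Table 4 only.
3. Make the Figure 2 note, Table 3 footnote e and Section 7.4.4.3 refer to Table 4 without frequency wording of their own.
4. Make any Investigator discretion consistent with the documented-agreement rule that follows Table 4.

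Which frequency applies is for the sponsor's clinicians, and none is proposed here. The cost is protocol wording only; no SAP analysis changes.
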